**Aim 2. To determine preliminary effects of neurofeedback on neural activation and emotional experience during the dyadic social interaction. Hypothesis 2A.** Mothers' own aIC activation while listening to their daughters will be positively correlated with that of their daughters' during the mothers' response. **Hypothesis 2B.** Stronger temporal synchrony and coupling between mothers' and daughters' aIC activation during the reflection condition will be associated with more validating statements made by the mother during the task and lower self-report ratings of negative emotions in both participants.

**Aim 3. To identify short-term effects of neurofeedback training. Hypothesis 3A (Exploratory).** Mothers' and daughters' neural activation of resting-state networks will be more temporally synchronous at the end of the hyperscanning session (following neurofeedback), as compared to their first resting-state fMRI scans in the hyperscanning session. **Hypothesis 3B.** Ratings of positive emotions will be higher and negative emotions will be lower following the hyperscanning session as compared to ratings taken before the scan.

[figure not shown]
The expected outcome of the proposed study is a rt-fMRI neurofeedback-hyperscanning protocol that will be available for implementation in future studies with larger samples in order to study its effects on adolescent depression. The protocol and data from the first five dyads will be used for a K award submission in the fall of 2019. A manuscript will be prepared and submitted following the end of data collection in the summer of 2020. The protocol developed in this study will provide the foundation for future prevention and intervention efforts aimed at the effects of parenting on the development of emotion regulation skills and depressive symptoms.

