**Table 2: Inclusion/Exclusion Criteria**

Criteria	Moms	Girls
Inclusion		
Eligible for fMRI	✓	✓
Sufficient English fluency to complete tasks	✓	✓
BMI	18.0-40.0	16.0-40.0
Right-handed	✓	✓
Biological female	✓	✓
Biological mother	✓	
Co-residing at least 4 days/week	✓	✓
Primary caregiver > 50% of child's lifespan	✓	
Age 13-17		✓
Exclusion		
Current psychiatric diagnosis	x	x
Medications influencing fMRI	x	x
Medical conditions influencing fMRI	x	x
Alcohol or psychoactive drug on scan day	x	x
Neurodevelopmental delay		x
History of mood or psychotic disorder		x
History of OCD or ADHD		x

different rates, with some studies indicating a gap in brain maturation due to the onset of puberty occurring two years earlier for girls; (3) many adolescents do not have a consistent father figure in the home, with rates of 1 in 4 children living in single mother families; and (4) mothers and fathers diverge in emotion socialization techniques and parenting styles that could impact results.

**fMRI hyperscanning.** All hyperscanning experiments will be conducted on two MR750 3T MRI scanners with fMRI imaging protocols and parameters described elsewhere. Prior to scanning, participants will complete a brief training session in the mock scanner to desensitize them to the MRI environment and to practice talking while remaining as still as possible. After this training, subjects will complete an 8-minute eyes-open resting-state scan followed by the dnf training and transfer runs. Subjects will then undergo a second resting-state scan and complete post-scan emotion rating scales.

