**Emotion Discussion with Dyadic Neurofeedback Task.** This task will be completed in the scanner using simultaneous hyperscanning data collection. Prior to the fMRI, adolescents (without the parent present) will be asked to think of recent situations when they were feeling strong negative emotions, such as anger, sadness, and/or anxiety. They will be informed that they will be talking to their mother about each situation during the scan. The mother (without the daughter present) will be provided with task instructions and informed that while talking to her daughter she will be receiving neurofeedback from a region in her daughter's brain. The mother will be told that her goal is to decrease activation in that region by calming her daughter and decreasing the intensity of her daughter's emotional response. The emotion discussion task will consist of four types of trials, each lasting 40s: Rest trials, Count trials, Discussion trials, and Reflection trials. During the first Discussion trial, the adolescent will describe the emotional situation. This will be followed by a second Discussion trial during which the mother will respond to the adolescent while receiving neurofeedback from the adolescent's aIC. This will be followed by a Count trial during which participants will mentally count backward from 300 by a number specified on the screen (for example, by 6: 300, 294, 288...) in order to bring aIC activation back to baseline. This will be followed by a 40s Rest period. Following the Rest trial, the adolescent will be provided 40s to respond to her mother (no neurofeedback presented), and the mother will subsequently respond again to the adolescent while receiving neurofeedback from her daughter's aIC. This will again be followed by a Count and Rest trial. Finally, both the adolescent and her mother will be asked to mentally (i.e., silently) reflect on the discussion while receiving neurofeedback representing the synchrony between both participants' aIC activation. This will be followed by another 40s Count trial and 40s Rest trial, for a total runtime of 8 minutes. Participants will complete three runs of the emotion discussion task with dnf, followed by a fourth transfer run in order to determine if the effects of the training persist. During the transfer run, the task will be exactly the same except no neurofeedback will be presented.

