**Hypothesis 1B.** *Mothers and daughters will be able to establish and maintain temporal synchronous aIC activation while reflecting on their interaction.* Correlations will be calculated between mothers' and daughters' aIC timecourses (Reflect vs Rest contrast).

**Hypothesis 2A.** *Mothers' own aIC activation while listening to their daughters will be positively correlated with that of their daughters' during the mothers' response.* The correlation between the mothers' and daughters' average beta weights for aIC activation during each participant's Listen trials will be calculated.

**Hypothesis 2B.** *Stronger temporal synchrony and coupling between mothers' and daughters' aIC activation during the reflection condition will be associated with more coded validation statements during the task and lower self-report ratings of negative emotions in both participants.* a) Coupling will be measured as the correlation between timecourses for aIC activation as described in Hypothesis 1B, transformed to z-scores (Fisher's r-to-z transformation). b) Participants will be asked to rate the intensity of various emotions they felt during the scan (0-10 Likert scale). Correlations will be calculated between the z-scores (a) and 1) the number of validating statements made by the mother across the scan and 2) ratings of negative emotions (b).

**Hypothesis 3A (Exploratory).** *Mothers' and daughters' neural activation of resting-state networks will be more temporally synchronous at the end of the hyperscanning session (following neurofeedback), as compared to their first resting-state fMRI scans in the hyperscanning session.* Similarity of resting-state networks will be evaluated as described in Lee et al. (2017). ICA will identify intrinsic resting-state networks at the group level. On the individual level, a matrix of correlation coefficients for all possible pairs of resting-state networks will be created and transformed to Fisher's z, then vectorized and correlated between each pair of mother-daughter dyads to determine the level of synchrony within the dyad. A paired t-test will be conducted to determine if there is a significant difference between resting-state synchrony at the beginning versus end of the scanning session.

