**Hypothesis 3B.** *Ratings of positive emotions will be higher following the hyperscanning session as compared to ratings taken before the scan.* Paired t-tests will be conducted separately for mothers and daughters to determine if ratings of positive emotions (e.g., "happy," "calm") made on a 0-10 Likert scale before the scan differ significantly from those made after the scan.

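### Hypothesis 3B is stated for positive and negative emotions, but only the positive half has a planned pre/post test

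*Combined protocol and SAP*

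**What the plan says.** Under Aim 3, the Specific Aims give Hypothesis 3B as "Ratings of positive emotions will be higher and negative emotions will be lower following the hyperscanning session", compared with ratings taken before the scan. Of the two Aim 3 hypotheses, 3A is labelled exploratory and 3B is not.

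The ANALYSES section, under the same label, reads "Ratings of positive emotions will be higher following the hyperscanning session as compared to ratings taken before the scan". The method follows: "Paired t-tests will be conducted separately for mothers and daughters to determine if ratings of positive emotions" differ before and after the scan on a 0-10 scale. The two example items, happy and calm, are both positive.

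Negative ratings are analysed in one other place, ANALYSES, Hypothesis 2B. There, "Participants will be asked to rate the intensity of various emotions they felt during the scan", and the negative ratings are correlated with Fisher-transformed mother-daughter aIC coupling.

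On data collection, the APPROACH section lists emotion ratings at the 4-hour visit, and the fMRI hyperscanning paragraph adds: "Subjects will then undergo a second resting-state scan and complete post-scan emotion rating scales". Neither lists the items.

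**The concern.** The two statements of Hypothesis 3B do not match. An analyst working from ANALYSES would complete 3B without looking at change in negative emotions, and a reader of the aims would expect that change to be reported.

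The omitted half matters for interpretation. In the task, daughters describe situations of strong negative emotion such as anger, sadness or anxiety, and the mother is told that "her goal is to decrease activation in that region by calming her daughter and decreasing the intensity of her daughter's emotional response". A rise in happy or calm ratings does not show that anger, sadness or anxiety fell. The calm item touches the training goal only in part. Negative ratings could also rise, because the daughter recalls negative situations across four runs, and no planned analysis would show it. A favourable positive-only result could then be reported as support for 3B as a whole.

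Timing adds some weight. Data from the first five dyads are meant to feed a grant submission in fall 2019. A test of negative ratings added after those data have been examined would be a post hoc choice.

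**Working it through.** The documents give no power, alpha, effect size or standard deviation for Hypothesis 3B, so there is no stated figure to reproduce. The check is a comparison of text followed by a count.

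**1. Hypothesis 3B, side by side**

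| Element | Specific Aims | ANALYSES |
|---|---|---|
| Positive ratings, after vs before | Higher | Higher; paired t-test in each group |
| Negative ratings, after vs before | Lower | Not mentioned; no test |

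Both are current text and the ANALYSES sentences are complete, so neither redaction nor a broken table explains the gap. The other five hypotheses (1A, 1B, 2A, 2B, 3A) keep every outcome between the two sections. Only 3B loses one.

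**2. Does another analysis fill the gap?**

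- Hypothesis 2B uses negative ratings, but as a between-dyad correlation with coupling, and for emotions felt during the scan. It estimates no change from before to after.
- The exploratory analyses in APPROACH concern the Table 3 surveys, completed at the screening visit. These are not the 0-10 emotion ratings.
- The passages on emotion ratings in APPROACH and fMRI hyperscanning describe collection and specify no test.

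Planned pre/post tests of negative ratings: 0.

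**3. Count of comparisons**

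If each valence is a single score (assumed):

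- implied by the aims: 2 valences × 2 groups = 4
- planned in ANALYSES: 1 valence × 2 groups = 2
- missing: 4 − 2 = 2

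If items are tested one by one, p positive items give 2p planned tests, and q negative items leave 2q unplanned. The two positive examples alone would give 2 × 2 = 4 planned. The documents do not give q; for an assumed q of 1 to 4, 2q runs from 2 to 8. Planned negative tests are 0 under either reading.

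**4. Cost of adding the missing tests**

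This step assumes one score per valence, two-sided alpha 0.05 per test and independent tests; the last is a simplification. The chance of at least one false positive is 1 − (1 − 0.05)^k:

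- k = 2: 1 − 0.95² = 9.75%
- k = 4: 1 − 0.95⁴ = 18.5%

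With 10 pairs per group, the standardised paired difference detectable with 80% power is about 1.00 at alpha 0.05, and about 1.28 at alpha 0.05/4 = 0.0125. At alpha 0.05, power is 29% for a standardised difference of 0.5 and 62% for 0.8. Tests of either half can pick up only large changes, so the estimates and their intervals should carry the reading.

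**The case against.** The best reply is that this is a drafting slip in a small pilot. Protocol and SAP are one document. The aims already fix the outcome, direction and comparison for negative ratings, and the paired t-test in ANALYSES is an obvious model. A report that claimed 3B on positive ratings alone would be visibly incomplete against the aims. The missing exploratory label proves little, since hypotheses 1A to 2B do not carry it either. The instruction to the mother concerns her daughter's response during the conversation, so it says nothing about the mother's own ratings, and it concerns a different moment from ratings taken after the session. The documents describe no control or sham condition, so a pre/post change could not be attributed to neurofeedback. The feasibility criterion (a mean rating of at least 5 out of 10) is untouched.

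Most of this stands as to weight. The link to the training goal supports the daughters' half of the gap only, and the item-level counts are illustrative. None of it removes the defect. ANALYSES does not leave the test for negative ratings vague; it restates the hypothesis without them and gives a complete analysis of what remains. An analyst who follows it has done what was planned and has left half of a stated hypothesis untested.

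**Conclusion.** The concern holds, with high confidence. Hypothesis 3B covers negative emotions in the aims, and no pre/post test of them is planned for mothers or daughters. The count of zero rests on the text alone. The statement that 2 of 4 comparisons are missing assumes one score per valence, and the error rates and detectable differences assume an alpha that the documents do not give.

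This should be corrected, but it does not threaten the study. Aim 1 feasibility is unaffected, and the likely cause is an omission in ANALYSES. Whether negative items are rated before the scan cannot be settled from the documents: the aims imply it, but no item list is given.

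**What to change.** In ANALYSES, Hypothesis 3B:

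- Restore the two-part hypothesis from the Specific Aims.
- Apply the same paired before/after comparison to negative ratings, separately for mothers and daughters, and report mean changes with 95% confidence intervals.
- State whether each valence is one score or is tested item by item, and name the items.
- Report and conclude on the positive and negative halves separately.

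Before scanning, confirm that the pre-scan form carries the same negative items as the post-scan form, and add them if it does not. A missing pre-scan rating cannot be recovered later.

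If the negative half was dropped deliberately, amend the Specific Aims instead, so that 3B is not reported as covering negative emotions.

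The cost is a few sentences of analysis text and, at most, a few 0-10 items on an existing form for 20 participants. With one score per valence, the 3B tests rise from two to four. A multiplicity adjustment is optional in a pilot of this size, but the plan should say whether one is used.
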